9.3 Definition of Populations

All data analysis will use the intent to treat population and use all available data. There is no per protocol analysis planned.

9.4 Interim Analyses and Stopping Rules

9.4.1 Interim Analysis

There are no interim or futility analyses planned.

Data analysis of Phase 1 data will occur during and immediately after data collection in Phase 1.

Data analysis of Phase 2 data will occur after data collection in Phase 2.

9.4.2 Stopping Rules

This study will be stopped prior to its completion if: (1) the intervention is associated with adverse effects that call into question the safety of the intervention; (2) difficulty in study recruitment or retention will significantly impact the ability to evaluate the study endpoints; (3) any new information becomes available during the trial that necessitates stopping the trial; or (4) other situations occur that might warrant stopping the trial.

9.5 Outcomes

9.5.1 Primary/Proximal Outcome

Phase 1 is a pilot study to assess feasibility. The primary aims and outcome assessments are shown in Table 4 below.

Table 4. Targets for Phase 1 Pilot Study.		
Feasibility Area	Method of assessment	Target at each site
Recruit participants	Number recruited per month	Recruit 10 participants in 4 months.
Train yoga teachers to fidelity	Teacher fidelity scale	Each teacher demonstrates >80% fidelity on final 3 classes rated.
Randomize participants to intervention components and correctly administer these components	Randomization errors; receipt of incorrect intervention components	No errors/ incorrect components received in 2 nd half of participants randomized.
Collect follow-up assessments	Percent of follow-up assessments collected (for M1, M2, and M3)	≥ 70% with sufficient data collected on dosage; ≥ 70% of other follow-up assessments collected, including chart reviews

The proximal outcome of Phase 2 is yoga dosage received. This will be calculated by adding the total number of minutes per week in the study yoga class and total number of minutes per week in personal practice (or outside yoga classes). Research staff will take attendance at study yoga classes, and, in the event someone does not attend the entire yoga class, will record the number of minutes present in class. We will measure personal practice using the Weekly Yoga Journal.

9.5.2 Secondary/Distal Outcomes

Consistent with the U01 mechanism, our focus in this study is NOT on the distal outcomes; rather, it is on yoga dosage received. However, we will collect distal outcome data to demonstrate feasibility of data collection for future research. Distal outcomes include: Pain interference, Pain Severity, Quality of Life, Depression, Anxiety, Substance Use, Retention in OAT, and Opioid Craving. The primary outcome for a future efficacy study will be pain interference.

9.6 Data Analyses

Phase 1 Data Analysis: See Section 9.5.1

Phase 2 Data Analysis: We plan to assess 4 candidate intervention components for possible inclusion in an optimized intervention that will be evaluated in a future RCT. To do so, we will use a balanced factorial ANOVA illustrated in Table 2. Each component will have two conditions producing a $2^4 = 16$ cell design with 4 main effects, 6 possible 2-way interactions, 3 possible 3-way interactions, and 1 possible 4-way interaction. In a fully balanced design using effect coding (not dummy coding), all effects in the model are uncorrelated and the n for each condition for all effects is N/2 (i.e., 96 without attrition; 79 estimated with 17% attrition for this primary outcome). Note that specific cells are not compared against other specific cells.

We will use a general linear model with each candidate component coded using effect (1 vs -1) coding. Recruitment site, sex, age, and OAT type will be covariates. The pragmatic exigencies of field research will likely result in imperfect balance (e.g., individual cells may have slightly varying n). However, we anticipate only very small variations in cell sizes and thus estimated model coefficients will be nearly, but not perfectly, uncorrelated.

To augment traditional frequentist statistics and facilitate interpretation we will calculate the Bayes factor. Based on the observed data, a Bayes factor estimates the strength of evidence supporting one hypothesis (model) in favor of a competing hypothesis (model).³²

We will track which classes each participant attends, and who teaches each class. As a sensitivity analysis, we will include not only site as a fixed effect, but also teacher. We will include a dummy variable for each teacher to represent whether or not the participant had exposure to that particular teacher (i.e., took at least one class with that teacher).

Determination of Final Intervention Components:

Goal: To determine which components will be included in the final, optimized intervention package.

Components:

All participants: attendance at 1 class (with 2 time choices) per week; materials for personal practice

1. Personal practice videos featuring study yoga teachers
2. Initial and 1-month 1:1 session with a yoga teacher
3. Text messages cuing personal practice
4. Monetary incentives for class attendance

Once data collection is complete, we will convene a meeting (or conference call) to make decisions about which intervention components should be included in the final intervention package. Participants in this meeting will include:

1. MPIs and co-Is and consultant [name];

2. Selected NCCIH staff (e.g., PO); and
3. Selected yoga instructors

At this meeting we will review all data collected.

Step 1: For each intervention component, we will first review the main and 2nd order interaction effects from the factorial experiment on the primary outcome of number of yoga minutes per week. We assume data will be missing at random. Missing data will be addressed using multiple imputation by chained equations.³³ Because the goal is intervention optimization, retention of components will not be based on a single criterion. We will initially choose to include all components for which there is a main or sympathetic interaction effect with a) an effect size (SMD) of 0.40 (estimated, based on preliminary data, to be 31 mins of yoga per week) or greater favoring the component; OR b) $p < .10$ favoring the component OR c) if the estimated Bayes factor provides substantial or stronger evidence preferring the intervention hypothesis to the hypothesis of no treatment effect. (See below for more information on Bayes factor).

Special cases:

1. Of monetary incentives for class attendance, we will look specifically at class attendance. If monetary incentives increase class attendance, and do not decrease overall minutes of practice, we will choose to include.
2. 3rd and 4th order interactions may be tricky to interpret. We will look at them, but place priority on main effects and 2nd order interactions in making decisions.
3. It is possible that 2nd order interactions may be antagonistic where the combination of two or more components is less effective than would be expected based on the main effects alone. At the same time, there may be significant positive main effects for both components. In this case, we will examine graphical depictions of results in order to determine whether to include both of the two components in question.

Step 2: All components that pass Step 1 will then be examined in light of their feasibility and acceptability. Data that bear on feasibility and acceptability include:

1. Participants' responses to qualitative interviews
2. Yoga instructors' experiences (field notes)
3. Feedback from administrators/ clinicians at sites [from field notes (clinicians) and structured interviews (key administrators)]
4. Adverse events determined to be related to a given component
5. Number of 1:1 sessions attended (relevant for the 1:1 session intervention component only); use of personal practice videos (relevant for the personal practice video component only). We note that even one 1:1 session, or a small amount of use of personal practice videos, could have an impact on pain interference or other relevant outcomes.
6. % of follow-up assessments completed (not expected to be different between groups; we would consider a difference of 15% in proportion of participants observed at M3 to be of concern, and would likely be a statistically significant difference)

In determining feasibility, each component that passed Step 1 will be determined to be:

1. Acceptable and feasible without any changes.
2. There are minor changes that we judge do not affect the core nature of the intervention that we can make to increase acceptability and feasibility to a higher level (e.g., 1:1 meetings were scheduled for 45 minutes but everyone agrees that 30 minutes was adequate and even preferable).

3. Not acceptable/ feasible.

Step 3. All components that passed Step 1 and Step 2 will be included in the final optimized intervention. We will make minor changes to components if indicated in Step 2.

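### Does the incentive rule in Step 1 need a stated standard for what counts as a decrease in overall minutes?

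*Combined protocol and SAP*

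**What the plan says.** The primary Phase 2 outcome (section 9.5.1) is yoga dosage, formed by "adding the total number of minutes per week in the study yoga class and total number of minutes per week in personal practice" (outside yoga classes count with personal practice). Staff record attendance at study classes, and minutes present when someone attends only part of a class.

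Step 1 of the component decision (section 9.6) has a general rule: "We will initially choose to include all components for which there is a main or sympathetic interaction effect" that meets any one of three criteria. Criterion a is "an effect size (SMD) of 0.40 (estimated, based on preliminary data, to be 31 mins of yoga per week", or more, in the component's favor. Criterion b is p < .10 in its favor. Criterion c is a Bayes factor "preferring the intervention hypothesis to the hypothesis of no treatment effect". The same paragraph says that retention will not rest on one criterion alone.

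Special case 1 then treats incentives separately, looking at class attendance: "If monetary incentives increase class attendance, and do not decrease overall minutes of practice, we will choose to include". Special case 3, in the same list, speaks of significant positive main effects.

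The decisions are taken at a meeting after data collection: "At this meeting we will review all data collected". Step 2 follows: "All components that pass Step 1 will then be examined in light of their feasibility and acceptability".

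**The concern.** Special case 1 reads as a firm rule, but its second condition has no yardstick. Criteria a to c are all worded for evidence in a component's favor, and nothing in section 9.6 says what counts as a fall. Two readings are possible: any negative estimate blocks the component, or only a fall with p < .10 does.

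Total minutes vary widely compared with what one 60-minute class per week can add, so the reading could matter even when the attendance gain is clear. It would be chosen by people who can already see the results. Step 2 looks only at components that passed Step 1, so it could not bring Component 4 back. Section 9.2 also says that, in an optimization trial, a missed effect can do as much damage as a false one.

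Three smaller gaps sit beside this:
- The attendance summary (classes or minutes) is not named, and attendance is absent from the list in section 9.5.2: "Distal outcomes include: Pain interference, Pain Severity, Quality of Life, Depression, Anxiety, Substance Use, Retention in OAT, and Opioid Craving".
- The phrase for overall minutes is not the dosage term of section 9.5.1.
- The text does not say whether criteria a to c on total minutes stay open for Component 4.

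**Working it through.** **Inputs from the plan.** Analyzed n = 158, or 79 per level of each component (sections 9.2 and 9.6). SMD 0.40 corresponds to 31 min/week (section 9.6).

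**The plan's own power figure.** The standard error of an SMD is 2/√158 = 0.159. At two-sided alpha .10, power is Φ(0.40/0.159 − 1.645) = .81 for SMD 0.40 and Φ(0.50/0.159 − 1.645) = .93 for SMD 0.50. These match the stated figures of above .80 and above .90, so two-sided .10 is used below.

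**Scale.** SD of total minutes = 31/0.40 = 77.5. Standard error of the difference = 77.5 × 0.159 = 12.33 min/week. A fall reaches two-sided p < .10 when the estimate is below −1.645 × 12.33 = −20.3 min/week.

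**Second condition alone.** For a true change t, the negative-estimate reading blocks with probability Φ(−t/12.33), and the p < .10 reading with Φ(−1.645 − t/12.33).

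| True change in total (min/week) | Negative estimate blocks | p < .10 fall blocks |
|---|---|---|
| +6 | 31% | 2% |
| 0 | 50% | 5% |
| −12 | 83% | 25% |
| −31 | 99.4% | 81% |

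The row for zero depends on neither n nor SD. It would be the same in any trial.

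**Both conditions together.** The route requires an attendance gain first. Take that as z > 1.645 for class minutes, with the two estimates bivariate normal. The plan does not give the following, so they are assumptions: class-minute SD 30 or 20 (30 is the maximum if at most one 60-minute class is attended per week), correlation .2 to .7 between the estimates, and the true gains shown. The standard error for class minutes is 30 × 0.159 = 4.77 or 20 × 0.159 = 3.18.

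| True gain: class / total (min/week) | Class SD | Passes, negative-estimate reading | Passes, p < .10 reading | Gap (points) |
|---|---|---|---|---|
| +12 / 0 (full offset at home) | 30 | .43–.48 | .77–.80 | 32–35 |
| +12 / 0 (full offset at home) | 20 | .495–.50 | .935–.94 | 44 |
| +12 / +12 | 30 | .69–.74 | .81 | 7–12 |
| +12 / +12 | 20 | .82–.83 | .98 | 15–16 |
| +6 / +6 | 30 | .27–.33 | .35 | 2–8 |
| +6 / +6 | 20 | .44–.52 | .59–.60 | 8–15 |
| 0 / 0 (inert) | either | .03–.05 | .05 | under 2 |

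Given an attendance pass, the negative-estimate reading blocks an inert component 3–34% of the time and the p < .10 reading under 2%. In the full-offset case these become 40–50% and 1–5%.

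**The text around the rule.** Special case 1 sits inside Step 1, where every effect is judged by SMD, p < .10 or Bayes factor, and where special case 3 speaks of significance. Applying the same yardsticks in the unfavorable direction is the natural way to judge a decrease. Of the side gaps, attendance and minutes present are recorded under section 9.5.1, so either summary can be computed. Overall minutes fits the Step 1 outcome, total yoga minutes per week. Criterion a is stated as an SMD, with the 31 minutes only a translation for total dosage, so it can be applied to attendance.

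**The case for a change.** The strongest case for a change is that this is the trial's central decision and the rule cannot be executed exactly as written. Where the plan wants judgment it says so, as with the graphs in special case 3. Where it wants a threshold for concern it gives one, such as the 15% difference in Month 3 follow-up in Step 2. Swapping home practice for class is the very harm that the second condition guards against, so the full-offset row is not idle. A sentence would cost little, and the choice would otherwise be made with results in view.

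Much of this stands. The term is undefined, the full-offset gap is large, and the document does not settle whether criteria a to c stay open for Component 4. But full offset is the extreme case, and no section forecasts it. The rates describe one route only. The general rule covers all components, so an incentive that fails special case 1 may still enter through its main effect or a favorable interaction.

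Nor is there an obviously better rule to write in. Requiring a p < .10 fall leaves a true loss of 12 min/week unblocked 75% of the time, against 17% under the negative-estimate reading. For a loss of 31 min/week the figures are 19% and 0.6%. Which error to tolerate is for the sponsor to decide.

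**Conclusion.** This is missing detail in a decision that deliberately uses several criteria, and analysts can fill it sensibly from the text around it. No rule that the plan states is shown to give a wrong result. The 50% against 5% contrast is arithmetically right, but it describes sign rules against .05-per-tail tests in general, and only one condition of one route.

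Within the route, the choice of reading moves the pass rate by 7 to 16 points when a 12-minute class gain carries into total minutes, by 2 to 15 points for a 6-minute gain, and by under 2 points for an inert incentive. It reaches 32 to 44 points only under complete offset by lost home practice. These ranges rest on normal theory, n = 158, the plan's implied SD of 77.5, two-sided p < .10, and the assumed class-minute SDs, correlations and gains. An explicit threshold would exchange one kind of error for another without a clear gain, so the plan can stand as written.

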3.2.3 Blinding

Follow-up assessments will be conducted by research staff who are blind to which arm participants were randomized.

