7.3 Adverse Events and Serious Adverse Events

Adverse Event (AE) definition: An adverse event (AE) is any unfavorable and unintended diagnosis, symptom, sign (including an abnormal laboratory finding), syndrome or disease which either occurs during the study, having been absent at baseline, or if present at baseline, appears to worsen. Adverse events are to be recorded regardless of their relationship to the study intervention.

Serious Adverse Event (SAE) definition: A serious adverse event (SAE) is one that meets one or more of the following criteria:

- Results in death
- Is life-threatening (places the subject at immediate risk of death from the event as it occurred; includes a suicide attempt or drug overdose)
- Results in inpatient hospitalization or prolongation of existing hospitalization
- Results in a persistent or significant disability or incapacity
- Results in a congenital anomaly or birth defect

An important medical event that may not result in death, be life threatening, or require hospitalization may be considered an SAE when, based upon appropriate medical judgment, the event may jeopardize the subject and may require medical or surgical intervention to prevent one of the outcomes listed in this definition.

Study staff will record all reportable events with start dates occurring any time after informed Protocol Version 2.8

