consent is obtained at least until the final day of study participation. Each time participants attend a yoga class, we will inquire about injuries due to yoga. For all participants in either the Phase 1 or 2, at Month 3 (end of intervention), study staff will administer the SAFTEE in order to inquire about the occurrence of AE/SAEs during the previous 3 months. This allows us to systematically assess the number of adverse events, severity, and resulting impairment. Finally, any time a participant reports an adverse event to any staff member, a research assistant will contact the participant to ascertain information for recording of the adverse event. For adverse events ascertained by any of these three possible methods, the research assistant gets information on what happened, start and stop dates, severity, functional impact, interactions with healthcare professionals, perceived cause, and possible relation to study participation. With this information, site PIs or Co-Is, with input from MPIs if needed, will code severity, causal relationship, and whether the event was expected. If necessary, staff will seek further information from the participant or other sources before coding. AEs will be coded on a weekly basis. Any potential SAE will be immediately reviewed by one of the MPIs or site PIs (or a qualified designee in their absence) and coded; this coding will subsequently be reviewed by the Safety Monitoring Committee (SMC).

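### The one adverse-event item in the Step 2 component decision relies on component-level attribution that Section 7.3 does not define and that is weak for harm acting through more yoga; the randomised comparison is not planned

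*Combined protocol and SAP*

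**What the plan says.** Section 9.6 selects components in three steps. Step 1 looks at yoga minutes. At Step 2, "All components that pass Step 1 will then be examined in light of their feasibility and acceptability". Six kinds of data are listed for Step 2. Item 4 is the only one about harm as such: "Adverse events determined to be related to a given component". Item 6 is a between-group comparison of follow-up completion at Month 3, with a 15% difference treated as a concern. Components that pass both steps enter the package at Step 3.

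Section 7.3 sets out how events are collected and coded. For each event the research assistant obtains, among other things, "perceived cause, and possible relation to study participation". Site PIs or Co-Is then "will code severity, causal relationship, and whether the event was expected". The same section states that "Adverse events are to be recorded regardless of their relationship to the study intervention".

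Injury ascertainment is described in two ways. Section 7.3 says: "Each time participants attend a yoga class, we will inquire about injuries due to yoga". Table 1, Section 6.2.4 and Table 2 list yoga injuries weekly over the first three months. Separately, Section 7.3 has the SAFTEE given to all participants at Month 3.

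**The concern.** Item 4 needs a determination for each event: was it due to the videos, the 1:1 sessions, the texts or the incentives? Section 7.3 gives no category, rule or form that produces this answer. The relation it names is to study participation as a whole, and the coded causal relationship has no stated object.

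The second difficulty is one of method. Step 1 mainly retains components for raising yoga minutes, and Section 7 names mild physical injury as the only expected adverse event of yoga. If a text or a $15 incentive leads to more yoga and a strain follows, the natural case-level cause is yoga. The component acted one step earlier in the chain. An item that counts only component-related events would tend to miss this route, which is the most plausible physical harm of Components 3 and 4. Randomisation can show such an excess without any causal judgement on single cases, but Section 9.6 plans no such contrast for adverse events.

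At stake is whether a component that causes harm by raising dose could pass Step 2 without the relevant comparison having been looked at.

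**Working it through.** **The plan's own figures.** The documents give no event rate and no precision figure for adverse events. Their power statement in Section 9.2 supplies the sample size per level and the error rate used below.

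- Inputs: 158 analysed, so 79 per level; 96 per level without attrition (Section 9.6); two-sided alpha .10, the reading used here (Section 9.2 writes it as alpha/2 = .10).
- Power for a mean difference = Φ(d·√(n/2) − 1.645). With n = 79: d = .40 gives Φ(2.514 − 1.645) = .808; d = .50 gives Φ(3.143 − 1.645) = .933. Both agree with the stated > .80 and > .90.

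**What a randomised comparison of events could show.** The event rate without the component, p0, is assumed at 5%, 10%, 20% and 30%.

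- Power = Φ[(Δ − 1.645·se0)/se1], where Δ = p1 − p0, se0 = √(2·p̄(1 − p̄)/n), p̄ = (p0 + p1)/2, and se1 = √([p0(1 − p0) + p1(1 − p1)]/n).
- Example with n = 96, p0 = .10, Δ = .133: p̄ = .1665, se0 = .0538, se1 = .0529; (.133 − 1.645 × .0538)/.0529 = .84, so power = .80.
- 90% CI half-width at p0 in both levels = 1.645·√(2·p0(1 − p0)/96).

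| Assumed p0 | Detectable excess, 96 per level | Detectable excess, 79 per level | 90% CI half-width, 96 per level | Power for a doubling, 96 per level |
|---|---|---|---|---|
| 5% | 11.0 points | 12.4 points | 5.2 points | .37 |
| 10% | 13.3 points | 15.0 points | 7.1 points | .62 |
| 20% | 16.1 points | 17.9 points | 9.5 points | .92 |
| 30% | 17.4 points | 19.3 points | 10.9 points | > .99 |

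Detectable excesses are at 80% power and two-sided .10.

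**How large dose-mediated harm might be.** This is an illustration only. It takes the Step 1 benchmark of 31 min/week as the extra yoga, although that is an inclusion threshold and not an expected effect. It assumes that injury hazard is proportional to minutes, with an assumed mean of m min/week without the component.

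- p1 = 1 − (1 − p0)^((m + 31)/m).
- m = 60, p0 = .10: p1 = 1 − .90^1.517 = .148, or about 4.6 extra injured among 96.
- m = 60, p0 = .20: p1 = .287, or about 8.4 extra among 96.
- For m from 45 to 120 and p0 of .10 or .20, the excess runs from 2.4 to 11.4 points. Power of the randomised contrast runs from .13 to .57.

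**Injuries per yoga hour.** If harm acts only through more minutes, events and hours rise together and the ratio is about the same at both levels. This rate therefore cannot reveal that kind of harm. A count of participants with an event can.

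**Ascertainment.** If injuries are asked about at class attendance, the number of enquiries rises with attendance, which Component 4 pays for. Counts from that source would then differ between levels partly through detection. The Month 3 SAFTEE does not depend on attendance. The weekly report may not either, but the documents do not settle whether it is separate from the class query.

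**The case against.** The strongest reply is that the plan is wider than item 4. All events are recorded whatever their relatedness, and the decision meeting is to review everything collected. The Step 2 list is not closed, and interviews, instructor notes and clinician feedback could raise a harm. The Safety Monitoring Committee, weekly AE review and stopping rules also protect participants. A selected component goes on to a future trial, not into practice. All of this stands. It rules out reading item 4 as the only safety check in the study, or concluding that harm from a component could not come to light. It does not supply a planned comparison by component: none of these layers is described as making one.

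A reader might also infer that Section 7.3 makes no causal judgement that could reach a component. The text does not go that far. Perceived cause and causal relationship are recorded, and a coder could name a component. The gap is that nothing defines this.

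A reader might infer that blinding makes attribution impossible, because "Follow-up assessments will be conducted by research staff who are blind to which arm participants were randomized". That sentence covers follow-up assessors. Causality is coded by site PIs or Co-Is, and nothing says they are blind.

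Finally, texts and incentives would not look harmless in every case. Section 5.1 lists privacy loss, distress, pain and mild injury as risks of the components themselves, and an injury in a 1:1 session or during a study video could be attributed directly. The weakness concerns indirect harm, mainly for Components 3 and 4. That reviewers would attribute such injuries to yoga is a reasonable expectation, not something the documents show.

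**Conclusion.** The concern holds in this bounded form. The only adverse-event item listed in the component decision depends on an attribution that no procedure defines. That attribution is a weak instrument for harm acting through extra yoga. The randomised contrast suited to the question is not planned, although item 6 of the same list uses one for follow-up completion.

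The size of any missed harm cannot be derived from the documents. The illustration of 2.4 to 11.4 points rests on assumed event rates, assumed mean minutes, proportional hazard and the 31-minute threshold. The comparison would itself be imprecise, with detectable excesses of about 11 to 17 points at 96 per level under assumed rates of 5% to 30%. It adds evidence that attribution alone does not give, but it cannot certify a component as safe. The change should be made before the decision meeting; it does not put the primary analysis in doubt.

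**What to change.** 1. Rewrite Step 2 item 4 in Section 9.6: for each component, tabulate participants with a yoga injury, with any AE and with any SAE, regardless of relatedness, at the yes level versus the no level (about 96 versus 96), as differences with confidence intervals. State that the table is descriptive and that absence of a difference does not clear a component.
2. Base the comparison on ascertainment that does not depend on attendance: the Month 3 SAFTEE and the weekly injury report in Table 1, Section 6.2.4 and Table 2. List events found only through the class-attendance query separately. Reconcile Section 7.3 with those places so that it is clear whether the weekly report is asked of everyone.
3. Keep case attribution as supporting narrative, and either define component-level attribution in Section 7.3 or drop the term.
4. Injuries per yoga hour may be shown as a supplement, with a note that they cannot reveal harm acting only through more minutes.

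The cost is a short edit to Section 9.6, a clarification in Section 7.3 and one table. The AE and SAFTEE data are already to be collected. Whether the weekly injury report exists as a separate enquiry to all participants must be confirmed first. The downside is the imprecision shown above.
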